10.20. Appendix 20: Protocol Amendment History

This is an original protocol.

1. INTRODUCTION

This statistical analysis plan (SAP) contains definitions of analysis sets, derived variables, and statistical methods for all planned analyses of efficacy, safety, pharmacokinetics (PK), and immunogenicity of bermekimab. This SAP incorporates all analyses through the Week 20 final database lock (DBL) for the study 77474462ADM2003. Due to early termination of the study by the sponsor with only a small number of participants enrolled, listings will be provided for efficacy and safety data. No formal analyses will be performed.

1.1. Objectives and Endpoints

Objectives	Endpoints
Primary	
To evaluate the efficacy of 16 weeks of multiple IV doses of bermekimab, compared with placebo, in participants with moderate-to-severe AD	Proportion of participants with Eczema Area and Severity Index (EASI)-75 ($\geq 75\%$ improvement from baseline) at Week 16.
Secondary	
To evaluate the PK and immunogenicity of 16 weeks of multiple IV doses of bermekimab, compared with placebo, in adult participants with moderate-to-severe AD	
Analyses of the following at all applicable visits from Week 0 through Week 16:
 
 • Serum concentrations of bermekimab over time, including steady-state trough serum concentrations. • The incidence and titers of antibodies to bermekimab
To assess the safety and tolerability of 16 weeks of multiple IV doses of bermekimab, compared with placebo, in participants with moderate-to-severe AD	
 • Proportion of participants with TEAEs • Proportion of participants with treatment-emergent SAEs • Proportion of participants with AEs leading to discontinuation of study intervention. • Proportion of participants with AEs reasonably related to study intervention. • Proportion of participants with AEs of infusion-related reactions. • Proportion of participants with AEs of infections, including serious infections and infections requiring oral or parenteral antimicrobial treatment. • Proportion of participants with Clinically significant abnormalities in vital signs and laboratory tests.
To characterize additional assessments of efficacy of 16 weeks of multiple IV doses of bermekimab, compared with placebo, in participants with moderate-to-severe AD	Analyses of the following at applicable visits through Week 16 by visit, respectively:

Objectives	Endpoints
	
 Proportion of participants with both vIGA-AD of 0 or 1 and a reduction from baseline of ≥ 2 points Proportion of participants with improvement (reduction) of eczema-related itch NRS ≥ 4 from baseline among participants with a baseline itch value ≥ 4 Proportion of participants with EASI-90
Exploratory	
To further characterize efficacy of 16 weeks of multiple IV doses of bermekimab, compared with placebo, in participants with moderate-to-severe AD.	
 Improvement from baseline to Week 16 in SCORAD Change from baseline to Week 16 in DLQI Improvement from baseline to Week 16 in POEM Improvement from baseline to Week 8 in eczema-related itch NRS Improvement from baseline to Week 8 in eczema-related pain NRS Improvement from baseline to Week 16 in eczema-related pain NRS Improvement from baseline to Week 16 in itch as measured by the ADIS Proportions of participants with a PGIS score of 1 (none) or 2 (mild) at Week 16 Change from baseline to Week 16 in PROMIS-29 total score and sub-scores Improvement in Hand Dermatitis IGA from baseline to Week 16.
To assess the impact of treatment with 16 weeks of multiple IV doses of bermekimab, compared with placebo, on selected biomarkers.	Analyses of the following at all applicable visits from Week 0 through Week 16: 
 Changes in cellular and molecular PD biomarkers levels in skin and blood from baseline compared with placebo. Changes in skin barrier function from baseline compared with placebo.

Abbreviations: AD=atopic dermatitis; ADIS=Atopic Dermatitis Itch Scale; AE=adverse event; DLQI=Dermatological Life Quality Index; EASI=Eczema Area and Severity Index; IGA=Investigator Global Assessment; -IV=intravenous; NRS=numeric rating scale; PGIS=Patient Global Impression of Severity; PK=pharmacokinetics; PROMIS=Patient-Reported Outcomes Measurement Information System; POEM=Patient-Oriented Eczema Measure; SAE=serious adverse event; SCORAD=Severity Scoring of Atopic Dermatitis; TEAE=treatment-emergent adverse event; vIGA-AD=validated Investigator Global Assessment for Atopic Dermatitis.

1.2. Study Design

This is a Phase 2, double-blind, randomized, placebo-controlled, multicenter, interventional study designed to assess the efficacy, safety, pharmacokinetics (PK), pharmacodynamics (PD), biomarkers, and immunogenicity of multiple doses of bermekimab administered via IV infusion for the treatment of moderate-to-severe AD in adult participants. The participant population will be comprised of men and women ≥ 18 years of age, with moderate-to-severe AD, that has been present for at least 1 year before the first administration of study intervention, as determined by the investigator through participant interview and/or review of the medical history. Participants must also have a history of inadequate response to treatment for AD with topical medications or for whom topical treatments are otherwise medically inadvisable, an EASI score ≥ 16 , an IGA score ≥ 3 , and an involved percent body surface area (BSA) $\geq 10\%$ at both screening and at baseline. Participants must agree to apply moisturizers at least once daily for at least 7 days before randomization and continue the treatment throughout the study.

A target of 60 participants will be randomly assigned in this study. The study has 3 periods namely: a screening period of up to 4 weeks, a double-blinded placebo-controlled period of 16 weeks, and a Safety Follow-Up period of 4 weeks, which includes an End of Study (EOS) visit. The study will have 3 parts within the double-blinded placebo-controlled period that will run in parallel and/or staggered: A, B, and C.

All participants will receive a weekly IV infusion of either bermekimab or placebo, in a 4:1 randomization ratio. Part A will consist of 10 participants receiving bermekimab 800 mg IV weekly or placebo. Part B will consist of 30 participants receiving bermekimab 1200 mg IV weekly or placebo. An analysis of the data from all 10 participants of Part A and the first 10 participants of Part B will support optimization and selection of the bermekimab dose for Part C. Selection of the Part C bermekimab dose will be based on PK, PD, efficacy, and safety analysis. Part C will consist of 20 participants receiving bermekimab or placebo at a higher or lower dose (not < 800 mg) than Part B, but with a maximum dose of 2400 mg IV weekly.

The study also includes 4 mandatory skin biopsies (2 at baseline and 2 after dosing). All participants of Part A and the first 10 participants of Part B will have skin biopsies done at Week 0 (1 lesional and 1 non-lesional), and at Week 6 (2 lesional). The rest of the participants will be biopsied at Week 0 (1 lesional and 1 non-lesional), and at Week 16 (2 lesional). Instructions for the collection and shipment of these samples can be found in the biopsy collection manual.

All participants will have an extended in-clinic observation period of 4 hours during the first 2 infusions. In this period, vital signs will be taken at the following time points: 0 hour (start of infusion), 30 minutes, 1 hour, 1 hour and 30 mins, 2 hours (end of infusion), 2 hours and 30 mins, 3 hours, 3 hours and 30 mins, and 4 hours (post-infusion). Beyond the first 2 infusions, all participants will have a 1 hour infusion period and at least a 1 hour observation post infusion, as well as vital signs taken every 30 minutes.

[figure not shown]
An internal and independent DRC will be commissioned for this study to ensure the safety of the participants enrolled in this study. In addition, an interim analysis will be conducted when the 10th

participant of Part B reaches Week 6. The interim analysis will be used to inform the dose decision for Part C based on the safety, preliminary efficacy, PK and PD data accrued up to the interim analysis.

One planned database lock (DBL) will occur at the end of the study. Additional DBLs could be considered.

A diagram of the study design is provided in [Figure 1](#).

Figure 1: Schematic Overview of the Study

2. STATISTICAL HYPOTHESES

The hypothesis for this study is that intravenous (IV) bermekimab treatment is superior to treatment with placebo as assessed by the proportion of participants achieving EASI-75 ($\geq 75\%$ improvement from baseline) at Week 16.

The null hypothesis to be tested to address the primary objective of this study is that there is no difference between any of the bermekimab doses (800 mg, 1200 mg, or Dose C) and placebo treatment based on the primary efficacy endpoint.

3. SAMPLE SIZE DETERMINATION

This study is designed to enroll approximately 60 participants in order to have sufficient power to detect a difference between the participants receiving bermekimab and the participants receiving placebo for the primary endpoint of the proportion of participants achieving EASI-75 at Week 16.

The EASI-75 response rate in the bermekimab 400 mg qw group was approximately 70% at Week 7 from the open label study (2018-PT044 [NCT03496974]). The EASI-75 response rates

in placebo group at Week 16 were 15% and 12%, in the 2 Phase 3 trials of dupilumab vs placebo in the treatment of adult participants with moderate-to-severe AD (Simpson 2016).

The EASI-75 response at Week 16 is assumed to be 15% for placebo, and 65% to 70% for the bermekimab treatment population (Table 1). Based on these assumptions, approximately 60 participants (10 in Part A, 30 in Part B, and 20 in Part C) are planned to be randomized. In each Part, participants will be randomized in a 4:1 ratio to bermekimab or placebo. Thus, there will be 8 participants in the bermekimab 800 mg group, 24 participants in the bermekimab 1200 mg group, 16 participants in the bermekimab C dose, and 12 participants total across the placebo groups.

These sample sizes provide the study with at least 80% power to detect a treatment difference between the each bermekimab intervention group and the pooled placebo intervention group in EASI-75 at Week 16 based on a Fisher's Exact test at a Type I error rate of 0.1 (2-sided).

Table 1: Power to detect a treatment difference in EASI-75 at Week 16*

Placebo	Bermekimab	Difference	Power
Bermekimab 1200 mg (n=24) vs placebo (n=12)			
15%	65%	50%	85%
15%	70%	55%	92%
12%	60%	48%	83%
12%	65%	53%	90%
12%	70%	58%	96%
Bermekimab dose C (n=16) vs placebo (n=12)			
15%	70%	55%	86%
15%	75%	60%	92%
12%	65%	53%	83%
12%	70%	58%	91%

EASI=Eczeema Area and Severity Index.

*Power is not calculated for Part A due to small sample size.

4. POPULATIONS (ANALYSIS SETS) FOR ANALYSIS

The populations for analysis are defined in Table 2 below.

Table 2: Description of analysis sets used to analyze the data in the study

Analysis Sets	Description
Enrolled	All participants who sign the ICF.
Randomized Analysis Set	The randomized analysis set includes all participants who were randomized at Week 0 in the study.
Full Analysis Set (FAS)	The full analysis set (FAS) includes all participants who were randomized at Week 0 and received at least 1 dose of study intervention.
Safety	The safety analysis set includes all participants who received at least 1 dose of study intervention.

5. STATISTICAL ANALYSES

5.1. General Considerations

The statistical analyses will include all analyses from Week 0 through Week 20 (the final safety follow-up).

In general, baseline is defined as the last observation prior to or at the time of the first study agent administration, unless otherwise specified.

5.1.1. Visit Windows

Nominal visits will be used for all by-visit analyses in the study. The study visits scheduled post randomization should occur at the times delineated in the Schedule of Activities. The study visits through Week 20 should occur within \pm 3 days of the scheduled visit.

5.1.2. Polling Algorithm for Analysis Centers

Unless otherwise specified, data from all investigational centers/sites will be pooled for analyses.

5.1.3. Reference Date, Study Day and Relative Day

The Reference Date is the date of the first study agent administration. If the date of the first study agent administration is missing or the first study agent administration is not done, then the Reference Date equals the corresponding visit date (eg, Week 0 visit date). If the corresponding visit date is also missing, then the Reference Date equals the randomization date. Study day is defined as the number of days from the study reference date to the event/visit date. It will be calculated as follows:

- If the event/assessment occurs on or after the reference date, then study day = event/assessment date – reference date + 1.
- If the event/assessment occurs before the reference date, then study day = event/assessment date – reference date.

Hence, the day of reference date is Study Day 1; the previous day is Study Day -1.

5.2. Participant Dispositions

Listings of participants will be provided for the following categories:

- Participants who discontinued study intervention
- Participants who terminated study prematurely
- Participants who were unblinded during the study period
- Participants who were randomized yet did not receive study intervention.

5.3. Primary Endpoint Analysis

5.3.1. Definition of Endpoint(s)

The primary efficacy endpoint is the proportion of patients achieving an EASI-75 response at Week 16. The EASI is a validated measure used in clinical practice and clinical trials to assess the severity and extent of AD. Four AD disease characteristics (erythema, thickness [induration, papulation, edema], [excoriation], and lichenification) will be assessed for severity by the investigator or designee on a scale of “0” (absent) through “3” (severe). In addition, the area of AD involvement will be assessed as a percentage by body area of head, trunk, arms, and legs and converted to a score of 0 to 6. In each body region, the area is expressed as 0, 1 (1% to 9%), 2 (10% to 29%), 3 (30% to 49%), 4 (50% to 69%), 5 (70% to 89%), or 6 (90% to 100%).

For each region, severity score is the sum of intensity for each of four signs.

- Severity score = Erythema + Edema/Papulation + Excoriation + lichenification intensity

For each region, multiple the severity score by the region score and by a multiplier. The multiplier is different for each body site.

- Head and neck: severity score x region score x 0.1
- Trunk: severity score x region score x 0.3
- Upper extremities: severity score x region score x 0.2
- Lower extremities: severity score x region score x 0.4

Add up the total scores for each region to determine the final EASI score. The minimum EASI score is 0 and the maximum EASI score is 72.

EASI-100 responder is defined as a 100% improvement from baseline in EASI total score (EASI score=0).

EASI-90 responder is defined as at least a 90% improvement from baseline in EASI total score.

EASI-75 responder is defined as at least a 75% improvement from baseline in EASI total score.

EASI-50 responder is defined as at least a 50% improvement from baseline in EASI total score.

5.3.2. Analysis Methods for Primary Endpoint

Due to the early termination of the study, the primary endpoint of EASI-75 response at Week 16 will be listed. No formal analyses will be performed.

5.4. Secondary Endpoints Analysis

5.4.1. Definition of Secondary Endpoints

5.4.1.1. Eczema Area and Severity Index

Details refer to section 5.3.1.

5.4.1.2. Validated Investigator Global Assessment for Atopic Dermatitis

The vIGA-AD™ developed by Eli Lilly and Company is an assessment instrument used in clinical studies to rate the severity of AD, based on a 5-point scale ranging from 0 (clear) to 4 (severe). The IGA score is selected using the morphological descriptors that best describe the overall appearance of the AD lesions at a given time point.

5.4.1.3. Eczema Skin Pain and Itch Numeric Rating Scale

The Eczema Skin Pain and Itch NRS is a two-item patient-reported outcome developed by the sponsor that participants will use to rate the severity of their eczema-related skin pain and eczema-related itch daily. Participants will be asked the following questions:

- Please rate the severity of your eczema-related **skin pain** at its worst in the past 24 hours.
- Please rate the severity of your eczema-related **itch** at its worst in the past 24 hours.

Each item is on a 0 to 10 NRS ranging from 0 “none” to 10 “worst possible” and will be scored separately. Participants will complete the rating scale daily from the screening visit through the last study visit as detailed in the protocol SoA.

The baseline is defined as the average score of last 7 days prior to Week 0 study agent administration. If there are more than 3 days missing data, then baseline is set as missing. Missing baseline will not be imputed.

Seven daily NRS scores are averaged into a weekly score (ie 7 days [from day -7 to -1] prior to a visit). Four days out of 7 days (either consecutive or nonconsecutive) are necessary to derive a weekly score; otherwise data are considered missing for that week.

5.4.2. Analysis Methods

The following secondary efficacy endpoints will be listed.

- The proportion of participants with both vIGA-AD 0 or 1 and a reduction from baseline of ≥ 2 points at Week 16.
- The proportion of participants with improvement (reduction) of eczema-related itch NRS ≥ 4 from baseline to Week 16.
- The proportion of participants with EASI-90 response at Week 16.

5.5. Exploratory Endpoints Analyses

5.5.1. Definition of Endpoints

5.5.1.1. Eczema Area and Severity Index

The definition of EASI score is described in section [5.3.1](#).

5.5.1.2. Eczema Skin Pain and Itch Numeric Rating Scale

The definition of NRS score is described in section [5.4.1.3](#)

5.5.1.3. Validated Investigator Global Assessment for Atopic Dermatitis

The definition of vIGA-AD is defined in section [5.4.1.2](#).

5.5.2. Analysis Methods

The following efficacy data from all participants in FAS will be included and listed by study intervention groups from Week 0 through Week 20.

- EASI
- vIGA-AD
- eczema-related NRS

5.6. Safety Analyses

All safety analyses will be performed using safety analysis set based on actual intervention received. No formal statistical comparison is planned.

5.6.1. Extent of Exposure

A list of study intervention administration through Week 15 will be provided.

5.6.2. Adverse Events

The verbatim terms used in the CRF by investigators to identify adverse events will be coded using the Medical Dictionary for Regulatory Activities (MedDRA). Any AE occurring at or after the initial administration of study intervention is considered to be treatment emergent. If the event occurs on the day of the initial administration of study intervention, and either event time or time of administration are missing, then the event will be assumed to be treatment emergent. If the event date is recorded as partial or completely missing, then the event will be considered to be treatment emergent unless it is known to be prior to the first administration of study intervention based on partial onset date or resolution date. All reported treatment-emergent adverse events will be included in the analysis.

Listings will be provided for treatment-emergent adverse events.

5.6.3. Clinical Laboratory Tests

The clinical laboratory parameters to be evaluated by the central laboratory include but are not limited to:

- **Hematology** will include but are not limited to the following: Basophils, Eosinophils, Hemoglobin, Lymphocytes, Monocytes, Neutrophils, Platelets, WBC, CRP and ESR.
- **Chemistry** will include but are not limited to the following: ALT, AST, Albumin, Alkaline Phosphatase, Bicarbonate (CO₂), Calcium, Chloride, Creatinine, GGT, Glucose, Potassium, SGOT, SGPT, Sodium, Total Bilirubin, Total Protein, Urea Nitrogen.

Participants in the safety analysis set with toxicity grades ≥ 2 will be listed.

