7. DISCONTINUATION OF STUDY INTERVENTION AND PARTICIPANT DISCONTINUATION/WITHDRAWAL

7.1. Discontinuation of Study Intervention

A participant's study intervention must be discontinued if:

- The participant withdraws consent to receive study intervention.
- The investigator believes that for safety reasons or tolerability reasons (eg, AE) it is in the best interest of the participant to discontinue study intervention
- Participants who experience a Grade ≥ 3 IRR should be discontinued from the study
- The participant has a serious adverse reaction that is related to an infusion of the study drug administration including a hypersensitivity reaction resulting in bronchospasm, wheezing and/or dyspnea that requires ventilatory support OR that results in symptomatic hypotension with a decrease in systolic blood pressure of 30% from a participant's baseline value or systolic blood pressure <90 mm Hg ([Sampson 2006](#)). In general, discontinuation of study intervention administration must be considered for participants who develop a nonserious but severe infusion-related reaction.
- The participant has a reaction resulting in myalgia and/or arthralgia with fever and/or rash (suggestive of serum sickness and not representative of signs and symptoms of other recognized clinical syndromes) occurring 1 to 14 days after an infusion of study intervention. These may be accompanied by other events including pruritus, facial, hand, or lip edema, dysphagia, urticaria, sore throat, and/or headache.
- The participant becomes pregnant or plans a pregnancy during the study period. Refer to [Section 10.5](#), Appendix 5: Contraceptive and Barrier Guidance.
- The initiation of protocol-prohibited medications, treatments, or interventions (outlined in [Section 6.8](#), Concomitant Therapy) that have an impact on AD efficacy evaluations.
- The participant has a malignancy including squamous cell skin cancer. Consideration may be given to allow participants, who develop ≤ 2 basal cell skin cancers and who are adequately treated with no evidence of residual disease, to continue to receive study intervention.
- A systemic opportunistic infection.
- A recurrent or chronic serious infection.
- The participant is deemed ineligible according to the following TB screening criteria:
 - A diagnosis of active TB is made.

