10.7. Appendix 7: Liver Safety: Suggested Actions and Follow-Up Assessments

Study intervention will be discontinued for a participant if liver chemistry stopping criteria are met.

Phase 2 Liver Chemistry Stopping Criteria and Increased Monitoring Algorithm

Phase 2 Liver Chemistry Stopping Criteria and Increased Monitoring Algorithm (no preexisting liver disease)

Abbreviations: ALT=alanine transaminase; AST=aspartate transaminase, INR=international normalized ratio; SAE=serious adverse event; ULN=upper limit of normal, Tbili=Total bilirubin.

Phase 2 liver chemistry stopping criteria are designed to assure participant safety and to evaluate liver event etiology.

Phase 2 Liver Chemistry Stopping Criteria and Follow-Up Assessments

Liver Chemistry Stopping Criteria	
ALT or AST-absolute	ALT or AST $\geq 3.5 \times$ ULN
ALT or AST Increase	ALT or AST $\geq 3 \times$ ULN persists for ≥ 4 weeks
Bilirubin^{1,2}	ALT or AST $\geq 3 \times$ ULN and total bilirubin $\geq 2 \times$ ULN
INR²	ALT or AST $\geq 3 \times$ ULN and international normalized ratio (INR) > 1.5
Cannot Monitor	ALT or AST $\geq 3 \times$ ULN and cannot be monitored weekly for 4 weeks
Symptomatic³	ALT or AST $\geq 3 \times$ ULN associated with symptoms (new or worsening) believed to be related to liver injury or hypersensitivity

Required Actions, Monitoring, and Follow-up Assessments

Actions	Follow-Up Assessments
Immediately discontinue study intervention 
 Report the event to the sponsor within 24 hours Complete the liver event/expedited reporting form, and complete an SAE eCRF if the event also met the criteria for an SAE² 	
 Viral hepatitis serology⁴ Obtain blood sample for pharmacokinetic (PK) analysis after the most recent dose⁵ Obtain serum creatine phosphokinase, lactate dehydrogenase,

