5.6.4. Vital Signs

Participants with markedly abnormal vital signs will be listed.

Table 3: Markedly Abnormal Vital Signs

Vital Sign	Criteria
Pulse	>[120] bpm and with >[30] bpm increase from baseline
	<[50] bpm and with >[20] bpm decrease from baseline
Systolic blood pressure	>[180] mm Hg and with >[40] mm Hg increase from baseline
	<[90] mm Hg and with >[30] mm Hg decrease from baseline
Diastolic blood pressure	>[105] mm Hg and with >[30] mm Hg increase from baseline
	<[50] mm Hg and with >[20] mm Hg decrease from baseline
Temperature	>[38]°C and with >=[1]°C increase from baseline
Respiratory rate	>[20] breaths per minute

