6.10. Appendix 10 Laboratory Toxicity Grading

The grading scale use for lab assessments is based on ‘Common Terminology Criteria for Adverse Events (CTCAE)’.

If a laboratory value falls within the grading as specified below but also within the local laboratory normal limits, the value is considered to be normal and will be reset to grade 0.

Pre-baseline measurements will use the same grading ranges as applied to baseline measurements. In case a test has two sets of ranges – one for baseline normal and one for baseline abnormal, the one for baseline normal will be applied for all measurements taken pre-baseline and on baseline.

Participants with toxicity grades ≥ 2 will be listed.

CTCAE Term	Grade 1	Grade 2	Grade 3	Grade 4	Janssen implementation notes
Blood and lymphatic system disorders					
Anemia	Hemoglobin (Hgb) <LLN - 10.0 g/dL; <LLN - 6.2 mmol/L; <LLN - 100 g/L	Hemoglobin (Hgb) <10.0 - 8.0 g/dL; <6.2 - 4.9 mmol/L; <100 - 80g/L	Hemoglobin (Hgb) <8.0 g/dL; <4.9 mmol/L; <80 g/L; transfusion indicated	Life-threatening consequences; urgent intervention indicated	Clinical signs and symptoms are not taken into consideration for grading.
Leukocytosis	-	-	>100,000/mm ³ ; >100 x 10 ⁹ /L	Clinical manifestations of leucostasis; urgent intervention indicated	Clinical signs and symptoms are not taken into consideration for grading; Added ranges in SI unit (x 10 ⁹ /L)
Investigations					
Activated partial thromboplastin time prolonged	>ULN - 1.5 x ULN	>1.5 - 2.5 x ULN	>2.5 x ULN; bleeding	-	Clinical signs and symptoms are not taken into consideration for grading.
Alanine aminotransferase increased	>ULN - 3.0 x ULN if baseline was normal; 1.5 - 3.0 x baseline if baseline was abnormal	>3.0 - 5.0 x ULN if baseline was normal; >3.0 - 5.0 x baseline if baseline was abnormal	>5.0 - 20.0 x ULN if baseline was normal; >5.0 - 20.0 x baseline if baseline was abnormal	>20.0 x ULN if baseline was normal; >20.0 x baseline if baseline was abnormal	Ranges defined for “abnormal baseline” are applied only if baseline > ULN. If baseline < LLN, then ranges for “normal baseline” are applied.

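### The SAP's only laboratory and vital-sign outputs are filtered listings, and the filters are less sensitive than the protocol's discontinuation thresholds for raised-baseline ALT or AST and for most systolic baselines

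*SAP*

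**What the plan says.** SAP section 1 and SAP Appendix 2 reduce the output to data listings because the study stopped early with few participants.

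- **Laboratory (SAP 5.6.3).** "Participants in the safety analysis set with toxicity grades ≥ 2 will be listed". In SAP Appendix 10, Grade 2 for ALT and AST is ">3.0 - 5.0 x ULN if baseline was normal" and ">3.0 - 5.0 x baseline if baseline was abnormal", with the note "Ranges defined for “abnormal baseline” are applied only if baseline > ULN".
- **Vital signs (SAP 5.6.4).** Only readings that meet Table 3 are listed. The low-systolic row is "<[90] mm Hg and with >[30] mm Hg decrease from baseline".

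The protocol sets its own action thresholds:

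- **Liver (Appendix 7).** "Study intervention will be discontinued for a participant if liver chemistry stopping criteria are met". The absolute criterion is "ALT or AST $\geq 3.5 \times$ ULN", with no reference to baseline. The other criteria start at 3 x ULN and add a condition: four weeks' persistence, raised bilirubin, raised INR, symptoms, or weekly monitoring not being possible. Inclusion criteria 17f and 17g admit AST and ALT up to 2 x ULN.
- **Hypotension (7.1, with the same limits in 8.2.7).** The rule covers "symptomatic hypotension with a decrease in systolic blood pressure of 30" percent from baseline, or a systolic pressure below 90 mm Hg. In 7.1 it sits inside a serious reaction related to an infusion.

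Protocol 9.4.4 planned the Grade 2 listing as an addition to descriptive statistics by time point, and planned vital-sign summaries over time. The SAP has dropped both sets of summaries.

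**The concern.** Once the summaries are gone, the filters decide which laboratory and vital-sign values anyone sees. Both were written without reference to the protocol's action thresholds. The liver filter moves with the participant's baseline while the stopping limit does not. The systolic filter joins two conditions with AND where the protocol joins its two with OR.

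Clinically significant abnormalities in vital signs and laboratory tests are a stated secondary endpoint (SAP 1.1). Infusion-related and hypersensitivity reactions are named risks (protocol 2.3), and vital signs are taken about every 30 minutes around infusions to look for them. In a small study reported by listings alone, individual values are the evidence. A value that crosses a protocol discontinuation threshold should not be absent from the laboratory or vital-sign output.

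**Working it through.** The plan states no figure to reproduce. The check compares thresholds directly.

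**Liver.** Let *b* be baseline ALT or AST and *v* a later value, both in multiples of ULN.

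1. The SAP lists that analyte when *v* > 3.0 x max(*b*, 1) (Appendix 10, Grade 2).
2. The protocol's absolute criterion is met when *v* ≥ 3.5 (Appendix 7).
3. The listing cut reaches the stopping limit when 3.0 x *b* = 3.5, that is *b* = 3.5/3 = 1.167.
4. For the persistent, symptomatic and cannot-monitor criteria the transaminase part is *v* ≥ 3, so the gap opens at any *b* above 1.

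| Baseline (x ULN) | Grade 2 starts above (x ULN) | Unlisted, ≥3.5 x ULN | Unlisted, ≥3 x ULN |
|---|---|---|---|
| ≤1.0 | 3.0 | none | exactly 3.0 only |
| 1.1 | 3.3 | none | 3.0 to 3.3 |
| 1.2 | 3.6 | 3.5 to 3.6 | 3.0 to 3.6 |
| 1.5 | 4.5 | 3.5 to 4.5 | 3.0 to 4.5 |
| 2.0 | 6.0 | 3.5 to 6.0 | 3.0 to 6.0 |

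Example: a rise from 2 to 5 x ULN is 5/2 = 2.5 x baseline. That is Grade 1 and unlisted, yet above 3.5 x ULN.

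**Combined liver criteria.** The listing is by participant and covers every graded analyte. With a normal baseline, bilirubin is Grade 2 above 1.5 x ULN, so the protocol's 2 x ULN is listed. With a raised baseline, Grade 2 starts above 1.5 x baseline, so 2 x ULN is missed only if baseline bilirubin is at least 2/1.5 = 1.33 x ULN. INR is Grade 2 above 1.5, the same cut as Appendix 7. These participants are therefore usually listed through the second analyte, provided, for INR, that it was measured; it is not in the routine panel (protocol 10.2).

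**Systolic pressure.** Let *b* be baseline and *s* a later reading, in mm Hg.

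1. Table 3 lists when *s* < 90 and *b* − *s* > 30.
2. The protocol's blood-pressure component is met when *s* < 90 or (*b* − *s*)/*b* ≥ 0.30.

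| Baseline | Reading | Fall | Fall, % | Protocol component | Table 3 |
|---|---|---|---|---|---|
| 110 | 85 | 25 | 22.7 | met (<90) | not listed |
| 140 | 98 | 42 | 30.0 | met (30%) | not listed |
| 100 | 70 | 30 | 30.0 | met (both) | not listed; fall is not above 30 |

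In whole mm Hg, for *b* below 120 the readings from *b* − 30 to 89 are missed: 80 to 89 at 110, and 70 to 89 at 100. A 30% fall leaves systolic at 90 or above once *b* reaches 90/0.7 = 128.6, and readings from 90 to 0.7*b* are then missed: 90 to 98 at 140. The two agree only for baselines of about 120 to 128. Every reading that passes the Table 3 row is below 90 and so meets the protocol component; the reverse fails.

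**The case against.** **The participant is not lost.** A reader might infer that someone who met a stopping rule could vanish from the report. The documents do not support that. Such a participant either stops, and is in the discontinuation listing (SAP 5.2), or continues, and is a major deviation for meeting withdrawal criteria without being withdrawn (SAP Appendix 4). Protocol 8.2 and 8.2.4 require clinically relevant changes to be recorded as adverse events, and SAP 5.6.2 lists all treatment-emergent ones. This stands. What remains is narrower: none of those listings is specified to show the transaminase or blood-pressure values.

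**The hypotension rule is not a bare blood-pressure limit.** Section 7.1 requires a serious, symptomatic reaction and 8.2.7 a symptomatic one. A reader might take an asymptomatic 110 to 85 as a stopping event; it is not. This also stands. The comparison is with the blood-pressure component only.

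**The combined liver criteria are mostly covered.** A reader might extend the gap to ALT with bilirubin or INR. As shown above, the second analyte usually brings the participant into the listing.

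**The Grade 2 filter is the protocol's own, and no passage says a reporting filter must match a stopping rule.** Both are true. But in protocol 9.4.4 that listing supplemented descriptive summaries; alone, it carries a load it was not designed for.

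**Few participants are affected.** Probably so. The documents give neither the number enrolled nor the baseline distribution, so no expected count can be stated. The liver gap needs a raised baseline and a substantial rise that stays within 3 x baseline. The systolic gap needs no unusual baseline.

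**Conclusion.** The point holds as a reporting gap. For ALT or AST above 1.17 x ULN at baseline, isolated values from 3.5 x ULN up to 3 x baseline meet the absolute stopping criterion and are unlisted; at the 2 x ULN entry limit the band is 3.5 to 6 x ULN. For the persistent, symptomatic and cannot-monitor criteria the band starts at 3 x ULN for any baseline above ULN. With a normal baseline, every value at or above 3.5 x ULN is listed. For systolic pressure, the Table 3 row misses readings that meet the protocol's blood-pressure component at baselines below 120 and at about 129 mm Hg or more.

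This rests on three readings: Appendix 10 is applied as written; baseline is the last value up to first dosing (SAP 5.1), with 2 x ULN taken as the top of the range because eligibility sets it; and no other output shows the values. The consequence is missing numbers in the laboratory and vital-sign output, not hidden participants or events. It does not bear on efficacy. It is worth correcting because it is cheap and concerns a stated safety endpoint.

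**What to change.** Keep both current listings and add two reporting filters.

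1. **SAP 5.6.3.** List every participant with any post-baseline ALT or AST at or above 3 x ULN, irrespective of baseline and CTCAE grade. Flag values at or above 3.5 x ULN. Show ALT, AST, alkaline phosphatase, bilirubin and, where obtained, INR over time.
2. **SAP 5.6.4.** As a reporting filter only, list systolic readings below 90 mm Hg, or falls of 30% or more from baseline, each on its own, cross-referenced to any infusion-related or hypotension adverse event.

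These close the gaps by construction, because they use thresholds already in the protocol. The cost is a few lines of SAP text and two filters on collected data. The drawback is a few more listed participants, including asymptomatic low-baseline readings such as 95 to 89; the cross-reference lets a reader set those apart. No change to the stopping rules is proposed, and no view is taken on which clinical threshold is right.
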